9.2. Treatment Satisfaction Questionnaire for Medication

TSQM is a health outcomes endpoint for Part 1 and a secondary endpoint for Part 2. TSQM is measured at baseline.

TSQM scores for Effectiveness, Side Effects, Convenience, and Global Satisfaction will be calculated for each visit as discussed in Section 6.7.6.2. The TSQM scores will be summarized by score, treatment, and visit with separate summaries for Part 1 and for the entire study period. For Part 1, MMRM will be used to compare each active dose to placebo for each time point. For this analysis, the TSQM CFB score of interest will be included as the dependent variable in the model with fixed effects for treatment, baseline event value, baseline TSQM score, visit, visit by treatment interaction and a random effect for subject included as independent variables. An unstructured covariance structure will be used.

Separate figures of Effectiveness, Side Effects, Convenience, and Global Satisfaction mean scores over time with one line per treatment group will be provided. There will be one set of figures for Part 1 and another for the entire study period. For the analysis at the end of Part 2, the figure will have separate lines for active treatment for subjects originally randomized to placebo, showing mean scores over time by treatment.

In addition, categorical summaries by treatment group and visit will be provided for responses to each individual question.

9.3. Work Productivity and Activity Impairment

WPAI is a health outcomes endpoint for Part 1 and a secondary endpoint for Part 2.

Absenteeism, presenteeism, work productivity loss, and activity impairment will be calculated as described in Section 6.7.6.3. WPAI scores will be summarized descriptively by treatment group and visit for Part 1 and for the entire study period. For Part 1, MMRM will be used to compare each active dose to placebo for each time point. For this analysis, the CFB WPAI score of interest will be included as the dependent variable in the model with fixed effects for treatment, baseline event value, baseline WPAI score, visit, visit by treatment interaction and a random effect for subject included as independent variables. An unstructured covariance structure will be used.

In addition, summaries statistics by treatment group and visit will be provided for responses to each individual question (Q2 to Q6) with a categorical summary provided for Q1.

Separate figures of each of the WPAI mean scores and CFB mean scores over time with one line per treatment group will be provided. There will be one set of figures for Part 1 and another for

the entire study period. For the plots produced at the end of Part 2, the figure will have separate lines for active treatment for subjects originally randomized to placebo.

10. SAFETY AND TOLERABILITY

Analysis of safety data will be conducted for the current study alone.

The safety analyses will be analyzed separately for Part 1; available data from all parts of the study will be combined for a long-term safety assessment.

10.1. Adverse Event Preferred Term and System Organ Class Summary Tables

The following are Part 1 safety endpoints and Part 2 primary endpoints:

- Number and proportion of subjects with a TEAE
- Number and proportion of subjects who discontinue due to a TEAE
- Number and proportion of subjects who experience a TESAE
- Number and proportion of subjects who experience a Grade 3 or 4 TEAE
- Number and proportion of subjects who experience a treatment-emergent Grade 3 or 4 laboratory abnormality.

In addition, the proportion of subjects with a treatment-emergent, treatment-related AE consistent with a drug rash will also be summarized

AEs will be mapped to the MedDRA version 19.1 preferred term (PT) and SOC. AEs are assessed by the investigator as Grade 1 (mild), Grade 2 (moderate), Grade 3 (severe), or Grade 4 (life-threatening) according to Division of Microbiology and Infectious Diseases (DMID) using the November 2007 criteria. If a subject experiences multiple events that map to a single PT, the greatest severity grade according to the DMID criteria and strongest investigator assessment of relation to study medication will be assigned to the PT for the appropriate summaries. All AEs will be listed for individual subjects showing both verbatim and preferred terms.

TEAEs are defined as AEs that occurred on or after first dose of study treatment, whether in Part 1 or Part 2, and will be assigned to the relevant treatment depending on when the TEAE began (Part 1 or Part 2 treatment). AEs occurring 30 days after the last dose for subjects who discontinue study treatment in Part 1 or up to 30 days after last dose in Part 2 will be considered as TEAEs and will be associated with Part 1 or Part 2 respectively. Note that investigators are not required to contact subjects after the last follow-up if it occurs prior to 30 days from last dose. All AEs that occurred prior to the initiation of study treatment or those recorded more than 30 days after the last dose of study treatment will be excluded from the tables but will be included in the listings.

Drug-related events are defined as those AEs that the investigator believes were possibly, probably, or definitely related to the study drug.

10.1.1. Summaries of Adverse Event Incidence Rates for All Subjects and Incidence Rates for Serious Adverse Events, Discontinuations due to Adverse Events, and Deaths

A brief summary of TEAEs will show, by treatment group, the number and percentage of subjects who 1) had any TEAE, 2) had any drug-related event, 3) permanently discontinued from study drug due to a TEAE, 4) had any TESA, 5) had any Grade 3 or higher TEAE, 6) had any Grade 3 or higher drug-related TEAE, 7) had any TEAE leading to interruption of study drug, or 8) had a drug-related TESA. This summary will be reproduced for TEAEs by month (1 month = 28 days) for the first 7 months of the study, eg Month 1 will include events which have a start date between Day 1 and Day 28 of the study, Month 2 will include events between Day 29 and Day 56, etc. Subjects at risk for each month will include those who are receiving drug in the period of interest or who have discontinued drug within 30 days of the start of the period. Figures presenting the categories by month will also be produced.

AEs will be summarized by treatment group. For each SOC and PT, the number and percentage of subjects reporting an event will be calculated. In summary tables, SOCs and events within a SOC will be presented by decreasing frequency count based on the total number of events. Multiple events (by subject or SOC as appropriate) will be counted only once per subject per dose in each summary. For summaries that use severity grade, the most severe event will be selected.

The following summary tables (number and percentage of subjects) of TEAEs (by SOC and PT) will be provided by treatment group:

- Overall summary of TEAEs
- Summary of TEAEs
- Summary of drug-related TEAEs
- Summary of TEAEs by severity
- Summary of treatment-emergent Grade 3 or Grade 4 AEs
- Summary of drug-related, treatment-emergent Grade 3 or Grade 4 AEs
- Summary of TESA
- Summary of TEAEs leading to permanent discontinuation of study treatment
- Summary of TEAEs leading to interruption of study treatment
- Summary of drug-related TESA

In addition, a summary of frequent AEs will be provided by PT (not by SOC and PT), in decreasing order of frequency. Frequent AEs will be defined as events that occur in 2 or more subjects in the clinical trial.

Data listings will be provided for all AE data. In addition to listing all AEs, distinct data listings will also be provided for the following:

- Grade 3 or Grade 4 AEs
- AEs leading to permanent study discontinuation

- SAEs (fatal and non-fatal)

A forest plot of most-frequent treatment-emergent AEs sorted by risk difference will be produced using the format recommended by the FDA/Industry/Academia Safety Graphics working group (<https://www.ctspedia.org/do/view/CTSpedia/StatGraphHome>).

A listing of subjects for whom narratives are required will be provided and will include the reason for the narrative.

10.1.2. Investigator-Identified Rash Events of Special Interest and Gastrointestinal Abdominal-Related Adverse Events

The following is a Part 2 primary endpoint:

- The proportion of subjects with a treatment-emergent, treatment-related AE consistent with a drug rash

All rashes, regardless of assessed causality or severity are reported as events of special interest (EOSIs) by investigators in a protocol defined manner. However, the endpoint of interest is the proportion of subjects with a treatment-emergent, treatment-related AE consistent with drug rash.

Gastrointestinal (GI) abdominal-related TEAEs are also of interest, although these are not EOSIs for investigator reporting purposes. There are no appropriate standardized MedDRA queries in MedDRA to evaluate GI abdominal-related AEs that are appropriate to assess potential AEs associated with BCX7353 use. To create a list of PTs that are pertinent, the events to be analyzed have been prospectively defined as all PTs within the MedDRA v19.1 hierarchy under the high-level group terms (HLGTs) of 1) gastrointestinal signs and symptoms and 2) gastrointestinal motility and defaecation conditions. See Section 17.3 for a detailed list of PTs, high level terms, and HLGTs. This selection is broad enough so that GI events are appropriately identified and analyzed but excludes terms that, although in the GI SOC, are not representative of the events of concern such as oral or esophageal events.

For the investigator-identified rashes and the GI abdominal-related events, separate listings will be provided. In addition, for both investigator-identified rashes and GI abdominal-related events there will be a summary that shows, by treatment group, the number and percentage of subjects with:

- A TEAE
- A drug-related TEAE
- Permanent discontinuation from study drug due to the TEAE
- An AE that was considered an TESAE
- Any Grade 3 or higher TEAE
- Any Grade 3 or higher drug-related TEAE
- Any TEAE leading to interruption of study drug
- A TEAE that was considered a drug-related TESAE
- A TEAE that required use of concomitant medication

For treatment-emergent investigator-identified rashes and GI abdominal-related AEs, time to development of the TEAE will be estimated using the KM method. The results will be displayed in summary tables as well as in a KM plot. Subjects who do not experience the event of interest will be censored at the date of the last dose. Summary displays for the investigator-identified rashes and GI abdominal-related TEAEs will include a count of the number of TEAEs as well as the number of subjects who experience each AE.

A KM plot and summary of duration of event will be provided for the investigator-identified rashes and GI abdominal TEAEs. The summary display will provide the median duration of event by treatment group, with the event as the unit of interest rather than the subject.

A separate analysis will be conducted in which the number and proportion of subjects with either a GI abdominal-related TEAE or an unconfirmed abdominal-only event is presented. The number of events will also be included in the summary.

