12.1.1. Definitions

12.1.1.1. Adverse Event

An AE is any untoward medical occurrence in a clinical study subject. No causal relationship with the study drug or with the clinical study itself is implied. An AE may be an unfavorable and unintended sign, symptom, syndrome, or illness that develops or worsens during the clinical study. Clinically relevant abnormal results of diagnostic procedures including abnormal laboratory findings (eg, requiring unscheduled diagnostic procedures or treatment measures, or resulting in withdrawal from the study) are considered to be AEs. If the diagnostic procedure prompts no additional treatment, visits, or monitoring, it will not meet the definition of an adverse event.

This includes the following:

- AEs not previously observed in the subject that emerge during the protocol-specified AE reporting period (see Section 12.1.2), including medical triggers resulting in an angioedema event. Emotional stress will not be considered an AE unless it results in a medical diagnosis or requires medical treatment.
- Findings from protocol-mandated interventions. This can include laboratory assessments performed in the course of the clinical trial. AEs should be reported only if the abnormalities are changes from baseline and are clinically significant as described above.
- Pre-existing medical conditions (other than the condition being studied) judged by the investigator to have worsened in severity or frequency or changed in character during the protocol-specified AE reporting period. When recording such events on an AE/SAE eCRF page, it is important to convey the concept that the preexisting condition has changed by including applicable descriptors (eg, "more frequent headaches").

An adverse reaction is defined in Article 2(n) of Directive 2001/20/EC as follows: all untoward and unintended responses to a study drug/IMP related to any dose administered. The definition covers also medication errors and uses outside what is foreseen in the protocol, including misuse and abuse of the product. The definition implies a reasonable possibility of a causal relationship between the event and the study drug/IMP. This means that there are facts (evidence) or arguments to suggest a causal relationship.

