12.1.1.3. Adverse Events of Special Interest

For this protocol, treatment-emergent maculopapular rashes that are deemed related to BCX7353 will be considered EOSIs. This does not include other types of rashes, such as urticaria or eczema. All treatment-emergent skin conditions should be reported as AEs but only maculopapular rashes deemed related to BCX7353 should be considered EOSIs.

An EOSI event in and of itself will not be considered serious unless it meets the seriousness criteria above. Events of maculopapular rash assessed as possibly, probably, or definitely related to BCX7353 regardless of severity must be reported to the sponsor medical monitor as described in Section 12.1.5.1. Management of BCX7353 drug-related rash is provided in Section 12.2.1.

12.1.2. Method, Frequency, and Time Period for Detecting Adverse Events and Reporting Serious Adverse Events

Reports of all AEs and SAEs, regardless of investigator attribution, are to be collected from the time of signing of the informed consent through to the last study visit (ie, through the posttreatment follow-up visit). All AEs and SAEs are to be reported in the AE eCRF.

AEs should be documented in the eCRF as investigators become aware of them. AEs are to be followed until the event resolves, as follows. If an event is ongoing at the last follow-up visit, Grade 1 and 2 events do not need to be followed if the event is deemed unlikely to be related or not related to study drug (see Section 12.1.3 for AE grading). For all Grade 3 and 4 events or events deemed at least possibly related to use of study drug, the event should be followed until the AE is resolved or the subject is in a clinically stable condition with regards to the AE.

The investigator shall report all SAEs immediately to the sponsor by communicating with the medical monitor (phone or email) and by entering the event into the AE eCRF and by completion of the SAE eCRF within 24 hours of their knowledge of the event (see Section 12.1.5). The SAE eCRF form is an additional form to the AE eCRF that provides important details on the SAE.

The investigator should follow all unresolved SAEs observed during the study until they are resolved, or are judged medically stable, or are otherwise medically explained.

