13.4.6. Analysis of Safety Variables

Analysis of safety data will be conducted for the current study alone.

The safety analyses will be analyzed separately for Part 1 alone; a later data analysis will evaluate long-term safety data for the current study.

Safety endpoints that will be summarized include, at a minimum, the number and proportion of subjects: 1) with a TEAE; 2) who discontinue BCX7353 due to a TEAE; 3) who experience a TESA; 4) who experience a treatment-emergent Grade 3 or 4 AE; and 5) who experience a treatment-emergent Grade 3 or 4 laboratory abnormality. In addition, the proportion of subjects with a treatment-emergent, treatment-related AE consistent with a drug rash as identified by the investigator will also be summarized.

Adverse events will be mapped to a Medical Dictionary for Regulatory Activities (MedDRA) preferred term and system organ class. The occurrence of TEAEs will be summarized using MedDRA preferred terms, system organ classifications, and severity. Separate summaries of TEAEs, TESAes, AEs considered to be related to study drug, and AEs leading to study drug interruption will be generated. All AEs will be listed for individual subjects showing both verbatim and preferred terms.

Descriptive summaries of vital signs, weight, bedside ECG parameters, and clinical laboratory results will be presented. Laboratory abnormalities will be graded according to the DMID Adult Adverse Event Table (Publish Date: Draft, November 2007; Appendix 16.1).

Any graded abnormality that occurs following the initiation of study drug and represents at least a 1-grade increase from the baseline assessment is defined as treatment emergent. The number and percentage of subjects experiencing treatment-emergent graded toxicities will be summarized. Laboratory toxicity shifts from baseline to worst postbaseline assessments will be summarized.

Clinically significant abnormal morphological ECG findings will be summarized.

The change from baseline in QTcF will be determined by routine ECGs. At each time point ECGs are analyzed, an individual subject's change from baseline will be calculated as:

$$\Delta_{ik} = (\text{QTcF for subject at time point } k - \text{Baseline QTcF})$$

Where QTcF measurements will be the average of triplicate ECGs at baseline and single values at each time point.

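### The TEAE definition in SAP 10.1 rests on onset timing alone and has no rule for an AE that starts in screening or on placebo and worsens on treatment

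*SAP*

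**What the plan says.** SAP 10.1 holds the only definition of a treatment-emergent AE in either document: "TEAEs are defined as AEs that occurred on or after first dose of study treatment, whether in Part 1 or Part 2". Each TEAE "will be assigned to the relevant treatment depending on when the TEAE began (Part 1 or Part 2 treatment"), with a 30-day tail after last dose. For the rest, "All AEs that occurred prior to the initiation of study treatment or those recorded more than 30 days after the last dose" "will be excluded from the tables but will be included in the listings". The list of changes from the protocol in SAP section 15 does not touch this.

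The Protocol describes an AE more broadly, as something "that develops or worsens during the clinical study" (12.1.1.1). AEs and SAEs "are to be collected from the time of signing of the informed consent" (12.1.2), and the screening period lasts 56 to 70 days (10.1). For graded laboratory abnormalities, a post-dose result that "represents at least a 1-grade increase from the baseline assessment is defined as treatment emergent" (13.4.6, repeated in substance in SAP 10.4).

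**The concern.** The usual purpose of a treatment-emergent definition is to capture both what starts on treatment and what gets worse on treatment. This one states only the first half. Two groups of events can fall through:

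- AEs that begin between consent and first dose, then worsen on study drug.
- AEs that begin on placebo in Part 1, then worsen after the subject moves to BCX7353 at Week 24. All placebo subjects who continue make that move.

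The counts at stake are any TEAE, discontinuation due to a TEAE, TESAE and Grade 3 or 4 TEAE. These are Part 1 safety endpoints and Part 2 and 3 primary endpoints; drug-related rash is a further primary endpoint in Parts 2 and 3. Long-term safety is the stated purpose of Parts 2 and 3, so the definition behind these counts should not depend on an unwritten data-entry habit.

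**Working it through.** The plan states no figure on this point, so there is none to reproduce. The check sets the passages side by side and then works out the weight of one subject.

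**1. Is worsening covered anywhere for AEs?** Protocol 12.1.1.1 treats a pre-existing condition that worsens during the AE reporting period as an AE. That period begins at consent, so the rule plainly covers conditions present before consent. It does not clearly reach an AE that first appears in screening or on placebo. Protocol 12.1.2 has AEs followed until they resolve, and tells the investigator to update the existing record once a diagnosis is made. It gives no instruction to open a new record when the grade rises.

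**2. Do the severity rules fill the gap?** SAP 10.1 takes the greatest grade when several events map to one preferred term. SAP 10.1.1 selects the most severe event and counts once per subject per dose. Both choose among events. Neither says which grade a single event carries when it changes over time.

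**3. How do the documents treat carry-over elsewhere?**

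- Laboratory grades: worsening counts (Protocol 13.4.6, SAP 10.4).
- Baseline for placebo subjects in adjusted-visit tables: reset before the first active dose (SAP 6.6).
- Medication continued from placebo into Part 2: counted again under the active column (SAP 7.7).
- AEs: no equivalent rule.

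**4. Weight of one subject.** Inputs: 8 placebo subjects planned (SAP 4.1) and 1:1 re-randomisation at Week 24 (SAP 4.4.2). Assuming that all continue and split evenly, 8 / 2 = 4 per after-placebo group, and 8 + 4 = 12 in the column that pools all subjects on one dose. One subject is then 1/8 = 12.5 points, 1/4 = 25 points and 1/12 = 8.3 points.

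**5. Illustration.** One placebo-onset Grade 1 or 2 event reaches Grade 3 on BCX7353, and the subject has no other Grade 3 or 4 event. Grade 3 or 4 TEAE counts:

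| Handling | Placebo | After-placebo dose | All on that dose |
|---|---|---|---|
| One record, original start date, onset grade kept | 0/8 | 0/4 | 0/12 |
| One record, original start date, maximum grade kept | 1/8 (12.5%) | 0/4 | 0/12 |
| New record at grade increase, or a worsening clause | 0/8 | 1/4 (25%) | 1/12 (8.3%) |

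Whichever grade a single record keeps, the active columns miss the event. For a screening-onset event that reaches Grade 3 in Part 1, a single record gives 0/8 in the subject's arm and a worsening clause gives 1/8, a shift of 12.5 points. This is the same in all three arms.

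**The case against.** The strongest reply is that the harm depends on a recording convention that the documents do not give. The Protocol's AE definition includes worsening. If sites enter a worsening as its own AE, it has a post-dose start date, and SAP 10.1 as written counts it under the drug being taken. The eCRF completion guide may say exactly this and is not among the documents. This stands: the consequences are conditional. It does not close the gap, because the only explicit instruction concerns pre-existing conditions and the follow-up rule fits a single continuing record at least as well.

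Four stronger inferences are tempting and are not supported:

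- **That a placebo-onset event is charged to placebo at its worst grade.** No passage says that a single record carries its maximum grade. That the placebo group has a TEAE of some grade is correct in any case, so its any-TEAE count does not change.
- **That both gaps favour the drug.** A worsened screening-onset AE is handled by the same rule in all three randomised, blinded arms. The undercount favours BCX7353 only if worsening is more common on drug, which would be an assumption.
- **That the events disappear.** They are missing from the TEAE tables only. The planned listings of SAEs, Grade 3 or 4 AEs and AEs leading to discontinuation are not limited to TEAEs, and the disposition table (SAP 7.1) gives reasons for every early discontinuation. In a trial of about 24 subjects with no safety hypothesis tests, a careful reader could find such a case.
- **That every safety endpoint is affected.** The Grade 3 or 4 laboratory endpoint already counts worsening, and the laboratory shift, liver-elevation and QTcF-change tables do not depend on AE onset.

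Listings do not repair a primary endpoint count, however. The endpoints are numbers and proportions of subjects, and those come from the tables.

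**Conclusion.** The gap is real and its consequences are conditional. SAP 10.1 defines and assigns TEAEs by timing alone, and neither document says how a grade increase in an ongoing AE is recorded. If the AE stays one record with its original start date:

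- a screening-onset AE that worsens on treatment is missing from the TEAE tables, in whichever arm it occurs;
- a placebo-onset AE that worsens on BCX7353 is not counted under the active dose. This is the part that clearly favours the drug.

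The number of affected subjects cannot be estimated. Study 302 reports a TEAE in 76.9% of placebo subjects, and 0.769 x 8 = 6.2. A reader might take that as about 6 of 8 subjects misassigned. It is only a rough size for the pool with any placebo-onset AE; the share still ongoing at Week 24, and the share that then worsens, are not given. What can be said is the weight of one subject: 12.5 points in a group of 8, and 25 points in an after-placebo group of about 4. That assumes the planned group sizes, an even split at Week 24, and no other qualifying event for that subject in that column.

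**What to change.** In SAP 10.1, define a TEAE as an AE with onset on or after the first dose of the treatment period, or an AE ongoing at that dose that later increases in grade, becomes serious, or leads to interruption or discontinuation of study drug. Assign the worsening to the treatment being taken when it happens, at the post-worsening grade, and leave the earlier grade with the earlier treatment.

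State the eCRF convention that makes this programmable: either a new record at each grade increase or dated grade changes within one record.

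Also state how events that begin or worsen in Part 3 are assigned. The assignment sentence names only Parts 1 and 2, while SAP 6.1 keeps subjects who move from 110 to 150 mg at Week 52 in their Part 2 treatment column with a footnote.

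The cost is SAP wording, a line in the eCRF guide, some data queries on AEs ongoing at first dose and at Week 24, and slightly higher TEAE counts. The change should be settled before the data are unblinded.

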- Subjects with a study drug-related Grade 3 or 4 rash as described by the Division of Microbiology and Infectious Diseases (DMID) criteria “skin-mucocutaneous” will be discontinued from study drug and treated according to best medical practice. All subjects with a suspected drug rash should undergo specific rash evaluation as described in Section 12.2.1. A Grade 3 rash is defined as vesiculation or moist desquamation or ulceration and a Grade 4 rash is defined as exfoliative dermatitis, mucous membrane involvement or erythema multiforme or suspected Stevens-Johnson syndrome or necrosis requiring surgery. Subjects with a Grade 1 or 2 study drug-related rash may be continued on BCX7353 if the investigator, subject, and sponsor deem it appropriate. The protocol for continuing BCX7353 in the presence of a rash is described in Section 12.2.1.

Subjects who discontinue from study drug in Parts 1 or 2 will be requested to complete all regularly scheduled visits and procedures outlined in Table 2 and Table 3 through the end of the study part (ie, Part 1 or 2) in which they were currently being treated. Subjects who discontinue in Part 1 will be requested to complete all regularly scheduled visits and procedures through Week 24. Subjects who discontinue in Part 2 will be requested to complete all regularly scheduled visits and procedures through Week 52. Subjects who discontinue in Part 3 will have an EOS visit 3 weeks after the last dose of study drug. All subjects who discontinue from all parts should be treated in accordance with local clinical practice for HAE.

If a subject who discontinues from study drug subsequently withdraws consent to continue study visits as previously outlined, please see Section 8.3.1.

Subjects are not eligible for treatment in Parts 2 or 3 if they discontinue study drug in Parts 1 or 2, respectively due to any of the above cited reasons.

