Part 3 of the study will start with the administration of the study drug dispensed at the Week 52 visit. Based on the safety profile and efficacy of the 150 mg dose in Part 1 of the similarly-designed Study 302, all subjects in the current study receiving 110 mg QD will be transitioned to open label 150 mg QD at the Week 52 visit.

[figure not shown]
Study visits in Part 3 will occur during Week 60 and approximately every 12 weeks thereafter, for a study duration of up to 104 weeks, until another mechanism is available to provide drug to the subject (eg, market access), or until the Sponsor discontinues development of the product for the prevention of angioedema attacks, whichever comes first. Telephone contact will occur at Weeks 56, 64, 68, 76, 80, 88, 92, and 100.

Subjects will continue to document all angioedema events that occur in their diary throughout Part 3 and will have regular visits to assess safety and tolerability. However, subjects will not be required to document compliance with the study drug. In addition, investigator and expert confirmation of angioedema events will not be required in Part 3. All angioedema events

recorded by the subjects will be reviewed and confirmed or rejected according to a set of pre-defined rules prior to inclusion in effectiveness analyses.

A final study follow-up visit will be scheduled approximately 3 weeks following the last administration of study drug (up to Week 104).

Figure 1: Study Schema

Abbreviations: e-diary = electronic diary; QD = once daily.

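### Time-to-event curves for rash and GI events count events up to 30 days after last dose but censor event-free subjects at last dose, which overstates incidence in the entire-study tail

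*SAP*

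**What the plan says.** SAP Section 10.1.2 says that for rash and GI abdominal-related events "time to development of the TEAE will be estimated using the KM method". For event-free subjects it adds: "Subjects who do not experience the event of interest will be censored at the date of the last dose".

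The event is the TEAE, defined in SAP Section 10.1. That section treats the following as treatment-emergent: "AEs occurring 30 days after the last dose for subjects who discontinue study treatment in Part 1 or up to 30 days after last dose" (the closing phrase refers to Part 2). Its outer limit is that AEs before first dose and "those recorded more than 30 days after the last dose of study treatment will be excluded from the tables". The 30-day window is named for Part 1 discontinuers and for Part 2. For Part 3 it can only be inferred from that general exclusion.

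Some post-dose observation is planned:
- Protocol Section 8.3.2: "Subjects who discontinue in Part 1 will be requested to complete all regularly scheduled visits and procedures through Week 24". Part 2 discontinuers are likewise asked to continue to Week 52.
- SAP Section 4.1: "A final study follow-up visit will be scheduled approximately 3 weeks following the last administration of study drug (up to Week 104").
- SAP Section 10.1 accepts that this may fall short of 30 days: "Note that investigators are not required to contact subjects after the last follow-up if it occurs prior to 30 days from last dose".

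The monthly TEAE summary in SAP Section 10.1.1 keeps subjects in the at-risk count if they stopped drug within 30 days of the start of the month.

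**The concern.** Events and censoring run on different clocks. A subject with a first rash 12 days after last dose contributes those 12 days and the event. A subject equally well observed for those 12 days without a rash contributes none of them. Post-dose person-time therefore enters the risk set only when it ends in an event. Section 10.1.1 uses a 30-day at-risk rule for the same class of events, so the SAP holds two risk sets, and nothing in it reconciles them.

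What is at stake is how two adverse events that the SAP singles out are described over the whole study. The outputs are Tables 14.3.1.25.ES and 14.3.1.39.ES and Figures 14.3.1.26.ES and 14.3.1.40.ES. A curve can fall to zero while most of the arm never had the event, contradicting the crude proportion reported beside it.

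**Working it through.** The documents give no figure for this analysis, so there is none to reproduce.

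**Estimator.** S(t) is the product, over event times up to t, of (1 − d/n), with d events among n at risk. *Written rule*: event-free subjects leave at last dose. *Matched rule*: they leave at the earliest of last dose + 30 days, last contact, and first dose of the next treatment where that closes the window.

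**Direction.** Both rules count the same events at the same times. At each event time the risk set under the written rule is contained in the matched one. Since 1 − d/n rises with n, S under the written rule is never higher. This needs no assumption about rates.

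**Worked examples** (n = 8, the planned arm size)

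1. Last dose Day 728 for all, follow-up 21 days (to Day 749), one first event on Day 740, none earlier. Written: n = 1, S = 1 − 1/1 = 0. Matched: n = 8, S = 1 − 1/8 = 0.875.
2. The same, with 4 of the 8 having earlier events, so S = 4/8 = 0.5 before Day 740. Written: 0.5 × (1 − 1/1) = 0. Matched: 0.5 × (1 − 1/4) = 0.375.
3. Part 1: one subject stops event-free on Day 60; another, already off drug, has an event on Day 75. Written: n = 7, S = 6/7 = 0.857. Matched: n = 8, because Day 60 + 30 = 90 is after Day 75; S = 7/8 = 0.875.

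**Chance of a drop to zero.** If m event-free subjects reach the end of dosing together and each has probability p of a first event in follow-up, the written rule gives S = 0 with probability 1 − (1 − p)^m. For m = 8: 1 − 0.99^8 = 7.7% at p = 1%, and 1 − 0.95^8 = 33.7% at p = 5%.

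**Simulation, entire study.** Assumptions: constant hazard, 10% discontinuation per 24 weeks, 21-day follow-up for everyone, one common planned end of dosing. Cells show written vs matched.

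| n | 24-week event rate | Mean final cumulative incidence | Excess (points) | S = 0 with event-free subjects |
|---|---|---|---|---|
| 8 | 2% | 9.57% vs 8.73% | 0.84 | 1.0% vs 0.1% |
| 8 | 5% | 22.08% vs 20.52% | 1.56 | 2.2% vs 0.2% |
| 8 | 10% | 39.12% vs 37.15% | 1.97 | 4.2% vs 1.0% |
| 8 | 30% | 80.54% vs 79.48% | 1.06 | 24.3% vs 20.9% |
| 24 | 2% | 11.15% vs 8.80% | 2.35 | 2.5% vs 0.02% |
| 24 | 5% | 24.85% vs 20.55% | 4.30 | 5.1% vs 0.01% |
| 24 | 10% | 43.29% vs 37.70% | 5.59 | 8.5% vs 0.04% |
| 24 | 30% | 82.09% vs 79.66% | 2.43 | 13.8% vs 3.2% |

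At Day 700 the excess is at most 0.48 points (77.78% vs 77.30%; n = 8, 30% rate). The distortion therefore sits almost wholly in the tail.

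**Simulation, Part 1** (n = 8). Discontinuation was set at 7.5% to 13%, guided by Study 302 in Protocol Section 5.3.1 (3/40 = 7.5%, 5/39 = 12.8% not completing). Event rates were 5% to 50%, the upper end guided by that study's 50.0% GI incidence at 150 mg. The largest excess at Day 168 is 50.62% − 49.86% = 0.76 points. The chance of a zero tail is 0.05% to 1.2%, nearly the same under matched censoring (0.05% to 0.96%).

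**The case against.** Censoring at last dose is a familiar on-treatment convention, and these displays carry no inference: Protocol Section 13.4.6 plans no safety hypothesis tests. The rash endpoint for Parts 2 and 3 is a proportion, which censoring does not touch. Events are also listed and counted, so a one-subject drop would be easy to recognise. All of this stands and limits the importance. It does not rescue the rule, because the convention is sound only when events are cut at last dose too.

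Four stronger readings are tempting but not supported:

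- *All 24 subjects at risk at about Day 729, so that matched censoring gives 23/24 = 0.958.* No planned active-treatment curve looks like this. Former placebo subjects have at most 80 weeks on active drug, and SAP Table 8 limits the placebo column to Part 1 data. About 8 per randomized arm, or 16 across both, could be at risk then, giving 0.875 or 15/16 = 0.938. The n = 24 simulation rows share this simplification.
- *The Part 1 curves are materially wrong.* They are not; see the Part 1 results.
- *Everyone is observed for three weeks after last dose.* Protocol Section 10.3.5.3 exempts subjects who move to commercial drug, and those who roll into the next part continue on drug. The mismatch applies to discontinuers and to subjects who attend a post-dose follow-up visit.
- *The 30-day window is written for Part 3.* It is a reasonable inference, not stated text.

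**Conclusion.** The rule is wrong as written, and its direction is certain: cumulative incidence of rash and GI events is never understated and sometimes overstated. Its size is small. In Part 1 it is under 1 point at Day 168. In entire-study curves the mean excess at the end is about 1 to 6 points: 0.8 to 2.0 for an arm of 8, and 2.4 to 5.6 for a stylised pool of 24. There is also an occasional collapse of the curve to zero.

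These sizes rest on an assumed constant hazard, 10% discontinuation per 24 weeks, 21-day follow-up for everyone and a common planned end of dosing. Staggered last doses, or transfer to commercial drug, would reduce them. GI incidence in Study 302 Part 1 (35.9% to 50.0%) lies above the simulated entire-study range; at the 30% rate the excess is already smaller than at 10%. The zero tail in an arm of 8 at the 30% rate is mostly due to small numbers, since it occurs in 20.9% of runs even with matched censoring.

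This is a minor point, worth correcting because it costs almost nothing.

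**What to change.** In SAP Section 10.1.2, make event inclusion and censoring use the same window. Either option works:

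- **(a)** Count only events with onset up to last dose and keep censoring at last dose.
- **(b)** Keep the 30-day window and censor event-free subjects at the earliest of last dose + 30 days, last contact, and first dose of the next treatment where the display is limited to one part or treatment. End the Part 1 curve at Day 168.

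Under (b) both limits matter. The last-contact limit covers follow-up that stops before 30 days, including transfer to commercial drug. Ending at Day 168 is needed because completers leave the Part 1 risk set at their first Part 2 dose. A Part 1 discontinuer with an event on Day 172 would then be alone at risk and drive the curve to zero under either censoring rule.

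In SAP Section 10.1, also state the TEAE window for Part 3.

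Cost: a few sentences in the SAP and a line or so of code. No new data are needed.
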